6.4 PELVIC / AORTIC LYMPH NODE DISSECTION

Surgeons will be required to perform pelvic ± para-aortic lymph node dissection as part of the treatment in both arms.

6.5 PREOPERATIVE SENTINEL NODE MAPPING WITH SPECT (Single Photon Emission Computed Tomography)

All consecutive patients who met the stage inclusion criteria stated in LACC protocol underwent preoperative lymphoscintigraphy followed by surgery at San Gerardo Hospital, Monza, Italy. The cervical injection was carried out by a gynecologist oncologist with the assistance of a member from the Nuclear Medicine Department the day of surgery or the day before (within 24 hours before the planned surgical intervention).

Pre-operative LSG was obtained following four injections of 0.5-1.0 mCi radiolabeled filtered 99mTc albumin nanocolloid in 1-4 ml volume, using 22 gauge spinal needles (0.7 x 90 mm) as suggested in LACC Trial protocol (6.3 page 28). Under direct visualization four submucosal injections of the radiotracer were performed slowly in each of the four quadrants of the uterine cervix. Following the injection, a 10 minutes planar anterior dynamic LSG (10 frames, 1 minute per frame) was carried out, followed by planar anterior static images, performed immediately after the dynamic acquisition. The SPECT/CT study was performed 3 hours after the radiotracer injection, with a hybrid system composed of a dual-head gamma camera with a low dose x-ray tube installed in its gantry (Infinia Hawkeye 4, GE Medical Systems). SPECT acquisitions of the lower abdomen and the pelvis were performed with the following parameters: matrix size 128 x 128, rotation 360°, 6° view angle steps 25 seconds time frame; the CT acquisition parameters were as follows: slice thickness 5.0 mm, axial acquisition with 5.0 mm interval, full per slice, velocity 2.6 RPM. Reconstruction parameters were as follows: matrix 512 x 512, pixel 1.10 mm, filters standard and extended FOV. Cross-sectional attenuation images in which each pixel represented the attenuation of the imaged tissues were generated. The overall acquisition time of a SPECT/CT study was about 20 minutes. Images were analyzed on a Xeleris Workstation (GE Medical Systems).

Blue-dye injection

Under general anesthesia and just before surgery all patients were injected with Methylene blue dye (Methylene Blue 1%, Bioindustria L.I.M, Novi Ligure, Italy). A total of 2 to 4 mL of blue dye (1-2 mL per

Version 4 October 2014 LACC Trial Page 34 of 105 injection) were injected into the cervix through a 20-gauge spinal needle at 3 and 9 o'clock position. The 12 o'clock injection was avoided to reduce the blue staining in the vesico-cervico-vaginal space, which makes the bladder dissection more difficult as recently suggested by Abu-Rustum et al (NR Abu-Rustum, F Khoury-Collado, ML Gemignani. Techniques of sentinel lymph node identification for early-stage cervical and uterine cancer. (Gynecol Oncol 2008; 111: S44–S50).

6.6 HISTOPATHOLOGIC EVALUATION OF THE SENTINEL NODES

Sentinel nodes will be classified according to a modification of the AJCC staging for axillary nodes from breast cancer as follows:

- 1) metastases present tumor greater than 2.0 mm in diameter;
- 2) micrometastases present tumor cell aggregates between 0.2 and 2.0 mm in diameter:
- 3) isolated tumor cells individual tumor cells or aggregates that are less than 0.2 mm in diameter, usually detected by immunohistochemistry; or
- 4) tumor absent no tumor cells identified in H&E (or immunohistochemically, if applicable) stained sections.

Non-sentinel lymph nodes will simply be reported as positive or negative for metastases based upon routine sectioning and examination of a single H&E stained section.

Grossing:

- All SLNs will be serially sectioned perpendicular to the long axis at 2.0 mm intervals. Lymph nodes 0.5 cm and smaller may be bisected.
- If the lymph node is submitted for frozen section (permitted but discouraged under most protocols), the lymph node should be submitted for frozen section as if it were being grossed routinely.
- Blocks are then submitted for routine processing.

Histologic examination, ultrastaging, and reporting:

- o If a SLN has a metastasis *in the initial H&E section*, no further work up is necessary on that lymph node. In a comment, state the size of the metastasis.
- o If a SLN is negative on the initial section, perform the ultrastaging protocol:
 - Five wide H&E levels at 200µm intervals. With each level, 2 unstained slides are cut (total of 10 unstained slides).
 - If the wide H&E intervals are negative, choose an unstained slide (usually the first

unstained with the first level) for immunostaining with pankeratin

- It is acceptable to release the ultrastaging results as an addendum report.
- Important note: In a case with multiple SLN parts (e.g. A-D) and one of the parts (e.g. part A) has a positive SLN but the other parts (e.g. B-D) are negative, the ultrastaging protocol is still performed on the negative parts (B-D); within a single part, if one SLN is positive (e.g. 1/7 lymph nodes positive), the ultrastaging protocol DOES NOT need to be performed on the remaining six negative SLNs in that part.

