3.3 RATIONALE FOR LYMPHATIC MAPPING

Published experience with the techniques for lymphatic mapping and sentinel lymph node detection in women with cervical cancer has been very limited. To date, no single study has enrolled more than 100 patients undergoing lymphatic mapping as part of their surgical treatment for cervical cancer. In fact, the majority of studies report on less than 50 patients. In addition, this procedure has not yet been shown to be viable in a multi-institutional setting. The limitations of previously published reports are important as these techniques are associated with a significantly high learning curve with early procedures less successful than later ones. This study will provide us the opportunity to enroll large numbers of patients for validation of intraoperative lymphatic mapping in women with cervical cancer in an international, multi-institutional setting.

3.3.1 DRUG INFORMATION:

Isosulfan Blue (Lymphazurin®)

- Formulation: Sterile aqueous solution in 5 ml vials.
- Preparation: None.
- Storage: Room temperature, avoid excess heat.

Supplier: Hirsch Industries, Richmond, VA 23230.

Adverse Effects: All adverse effects are allergic in nature and occur in <1% of patients. These

include localized swelling and pruritus of the hands, feet, abdomen and neck. Severe reactions

including edema of the face and glottis, respiratory distress, and shock have been occasionally

reported with other similar compounds. In rare instances, isosulfan blue can cause a transient

drop in oxygen saturation as measured by pulse oximetry. Isosulfan blue will turn the urine

blue-green for up to 24 hours following injection.

Contraindications: Known hypersensitivity to phenylethane compounds.

Methylene Blue

Formulation: Sterile solution of 1% methylene blue in water for injection in 1 ml and 10 ml vials.

Preparation: None.

Storage: Room Temperature (15-25 °C).

Supplier: Taylor Pharmaceuticals, Decatur, IL 62522.

Dose: Up to 4 ml subcutaneous. Not for IV use for this protocol.

Metabolism: Methylene blue is reduced in tissues to leucomethylene blue.

Adverse Effects: Subcutaneous necrosis has been reported at injection sites. In this study the

injection site is resected with the primary tumor. This complication has not been described in

lymphatic mapping studies. Allergic reactions such as rash, hives, or hypersensitivity reactions

have been described. They appear to occur in approximately 1% of patients.

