5.3 SCHEMA

6.0 STUDY TREATMENT

Given the extensive range of possible instrumentation for this procedure, the choice of instrumentation

for the laparoscopic or robotic approach will be left to the discretion of the surgeon.

At the commencement of surgery, a thorough inspection of all peritoneal surfaces should be performed

including direct inspection of the diaphragm. The location of any metastatic disease should be

documented in the operative report and a biopsy should be performed to confirm the diagnosis. If

intraperitoneal cancer is detected, the aim of treatment should shift to palliation and the radical

hysterectomy should be abandoned.

The pelvic lymphadenectomy may be performed before or after the radical hysterectomy and the

sequence choice will be left to the discretion of the physician. Decision planning regarding continuing

the radical hysterectomy based on intraoperative status of lymph nodes will be left to the discretion of

the physician. In patients undergoing sentinel node identification and lymphatic mapping, the choice of

that technique is left to the discretion of the individual surgeon.

Patients who undergo sentinel node identification will undergo a complete pelvic lymphadenectomy.

This includes common iliac lymph nodes. The time allocated to sentinel node identification should be

noted separately in the operative report.

In patients with macroscopic evidence of metastatic disease to the pelvic lymph nodes based on

intraoperative assessment, a complete pelvic lymphadenectomy is not required and the radical

hysterectomy may even be abandoned. Such patients should have a para-aortic lymph node sampling

to determine extent of disease, with this being at the discretion of the individual surgeon.

During the operative procedure, the surgeon should document the specific surgical instruments used in

patients randomized to the laparoscopic/robotic approach. The surgeon should also note in the

operative report the following information:

• Operative time from start of radical hysterectomy, as documented by skin incision, until all

trocar sites have been closed or abdominal incision is closed.

Version 4 October 2014 LACC Trial Page 26 of 105

- Blood loss
- Intraoperative complications
- Reasons for conversions to laparotomy in patients randomized to the laparoscopic or robotic approach

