10.3 ANALYSIS OF IOLM COMPONENT

The ability to successfully identify at least one sentinel lymph node in each patient undergoing radical hysterectomy and IOLM will be calculated. In addition, location, number, and laterality of identified sentinel node(s) will be reported. In patients where at least one sentinel node is identified, sensitivity, specificity, positive and negative predictive values of the procedure will be calculated.

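### Sentinel nodes are ultrastaged but non-sentinel nodes get one H&E section, so the planned sensitivity and NPV of mapping are biased upward relative to equal work-up

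*Protocol*

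**What the plan says.** Section 6.6 sets two pathology standards.

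- **Sentinel nodes.** "All SLNs will be serially sectioned perpendicular to the long axis at 2.0 mm intervals". They are classified down to micrometastases and isolated tumour cells. "If a SLN is negative on the initial section, perform the ultrastaging protocol": five further H&E levels and, if these are negative, a pankeratin stain.
- **Non-sentinel nodes.** "Non-sentinel lymph nodes will simply be reported as positive or negative for metastases based upon routine sectioning and examination of a single H&E stained section".

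Section 6.0 supplies the non-sentinel nodes: "Patients who undergo sentinel node identification will undergo a complete pelvic lymphadenectomy". Section 10.3 states the accuracy analysis: "In patients where at least one sentinel node is identified, sensitivity, specificity, positive and negative predictive values of the procedure will be calculated". Section 3.3 says the study will enrol enough women for "validation of intraoperative lymphatic mapping in women with cervical cancer", while sections 1.0 and 7.2 list the feasibility of sentinel node biopsy as a secondary objective and outcome.

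The protocol does not provide for ultrastaging of non-sentinel nodes when the sentinel nodes are negative. It does not say whether micrometastases or isolated tumour cells count as a positive sentinel node in section 10.3, and it does not say that accuracy will be based on the first H&E section alone.

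**The concern.** A false negative for mapping is a woman whose sentinel nodes are negative and whose non-sentinel nodes hold tumour. The test is therefore checked against the nodes that are examined least. If a small deposit in a non-sentinel node is missed, the woman moves from false negative to true negative. The same deposit in a sentinel node would probably have been found and credited to the technique. This is differential verification, and its direction is known: compared with equal work-up of all nodes, sensitivity and NPV can only rise.

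NPV is what a reader would use to judge whether a negative sentinel node can be relied on, so the error is toward reassurance. A later analysis plan can change how positives are defined, but it cannot recover non-sentinel disease that was never looked for.

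A smaller matter concerns specificity and PPV. If any positive sentinel node makes the woman node-positive, a false positive cannot occur and both equal 100% by definition.

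**Working it through.** The protocol gives no target sensitivity, target NPV or sample size for the mapping component, so there is no figure to reproduce. The check is a patient-level two-by-two table.

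**Inputs**

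- *Se* = 85%, the share of node-positive women with tumour in a sentinel node (assumption; section 2.2.1 cites 87.5%, 91% and 92% from earlier work).
- *f* = 20% to 50%, the share of node-positive women with low-volume disease only (assumption).
- Ultrastaging finds 95% of low-volume disease (assumption).
- *q* = 30% to 70%, the chance that one H&E section finds it (assumption).
- *p*, node-positive rate: 2% to 8% for stage IA2 or small IB1, up to 18% for IB1 (section 2.2.1).

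**Sensitivity**

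A = Se × [(1 − f) + 0.95f], true positives per node-positive woman.

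B = (1 − Se) × [(1 − f) + qf], false negatives actually seen.

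Apparent sensitivity = A / (A + B). Share of false negatives not counted = f(1 − q).

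| f | q | A | B | Apparent sensitivity | Rise (points) | False negatives not counted |
|---|---|---|---|---|---|---|
| 0.20 | 0.7 | 0.8415 | 0.1410 | 85.6% | 0.6 | 6% |
| 0.35 | 0.5 | 0.8351 | 0.1238 | 87.1% | 2.1 | 17.5% |
| 0.50 | 0.3 | 0.8288 | 0.0975 | 89.5% | 4.5 | 35% |

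**NPV, middle row**

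Equal work-up: (1 − p) / (1 − 0.85p). Under section 6.6: 1 − pB / (1 − pA).

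- p = 18%: 96.8% becomes 97.4%, a rise of 0.6 points.
- p = 8%: 98.7% becomes 98.9%, a rise of 0.2 points.
- p = 2%: 99.69% becomes 99.75%, a rise of about 0.05 points.

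**Other assumptions**

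Take sensitivity 87.5% from section 2.2.1 and assume ultrastaging misses nothing. If half of the false negatives are low-volume and one section misses all of them, apparent sensitivity is 0.875 / (0.875 + 0.125 × 0.5) = 93.3%. If it catches half of them, the figure is 0.875 / (0.875 + 0.125 × 0.75) = 90.3%. A harsher case (sensitivity 80%, three quarters of false negatives low-volume, none caught) gives 0.80 / (0.80 + 0.20 × 0.25) = 94.1%, a rise of 14 points. The bias vanishes only if no false negative is low-volume or one section catches all of them.

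**Does first-section H&E for both node types remove the bias?**

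In the middle case, first-section true positives are 0.85 × (0.65 + 0.5 × 0.35) = 0.70125 and false negatives are 0.15 × 0.825 = 0.12375. The ratio is 0.70125 / 0.825 = 85%, but only if *q* is the same in both node types and no woman has disease in both. Women positive only on sentinel ultrastaging number 0.85 × 0.35 × (0.95 − 0.5) = 0.13388. Suppose 10% to 30% of them also have an H&E-positive non-sentinel node (assumption). They then become false negatives:

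- 10%: 0.70125 / (0.70125 + 0.12375 + 0.01339) = 83.6%.
- 30%: 0.70125 / (0.70125 + 0.12375 + 0.04016) = 81.1%.

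The H&E-only figure can therefore err downward. In the other direction, 2 mm sectioning still favours the sentinel nodes on the first section.

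**Specificity and PPV**

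If a positive sentinel node defines node-positive status, the false-positive count is 0, so specificity = TN / (TN + 0) and PPV = TP / (TP + 0), both 100%.

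**The case against.** Four objections carry weight.

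*Positivity is undefined.* A reader might infer that micrometastases and isolated tumour cells are counted as true positives. Section 6.6 only sets reporting categories, and the definition may sit in an analysis plan that is not shown. This stands as a limit on the claim. It does not remove the point, because the unequal work-up is fixed in the protocol and limits what any analysis plan can do.

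*Ultrastaging may be part of the test.* Section 10.3 speaks of the procedure, and section 6.6 makes ultrastaging part of sentinel evaluation. This is a fair choice of index test, and finding more disease that way is legitimate. The reference nodes would still be less thoroughly examined, so the ultrastaging-inclusive figure should be kept but qualified.

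*Restricting to first-section H&E is not clean.* This stands, as the working shows. A reader might infer that such a restriction restores the true value; that holds only with equal first-section detection and no woman with disease in both node types.

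*The effect is modest and secondary.* Even if all 740 women were mapped and 18% were node-positive, there would be about 133 positives and a 95% half-width of 1.96 × √(0.85 × 0.15 / 133) = 6.1 points. Mapping is optional and section 6.8 excludes each institution's first three cases, so precision would be worse. The planned detection rate (at least one sentinel node found) is untouched. This limits the weight of the point, but a bias of known direction does not shrink as women are added.

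**Conclusion.** The point holds as a bias of certain direction and uncertain size. Sections 6.6 and 10.3 together bias sensitivity and NPV upward relative to equal work-up of all nodes. Under the main assumptions the rise in sensitivity is about 0.6 to 4.5 points, and the middle-case rise in NPV is about 0.6 points at 18% node positivity and close to nil at 2%. The low-volume share and the detection probabilities are assumptions; the protocol supplies neither.

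Two stronger readings should be resisted. A reader might infer that one H&E section cannot show small metastases at all; it can hit some by chance, so likely to be missed is as far as the text goes. A reader might also infer that the trial's main conclusion is affected; only the secondary mapping outcome is, not disease-free survival.

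**What to change.** Amend section 10.3 as follows.

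1. State which deposits (metastases, micrometastases, isolated tumour cells) make a sentinel node positive.
2. Report patient-level sensitivity and NPV twice: with ultrastaging included, and on initial-section H&E for both node types.
3. Tabulate separately the women positive only on ultrastaging, split by non-sentinel H&E status.
4. State that the ultrastaging-inclusive figures are biased upward because non-sentinel nodes were not ultrastaged. State also that the H&E-only figures are not fully symmetric because of 2 mm sectioning, and may count as false negatives women whose mapped node was positive only on ultrastaging.
5. State that specificity and PPV are 100% by definition if any positive sentinel node makes the woman node-positive.

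The cost is small. The initial section is already read before ultrastaging, so no new slides are needed. The first-section result must be recorded separately, and the second estimate rests on fewer positive women and has a wider interval. The change makes the bias visible but does not remove it.

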6.7 ADJUVANT RADIOTHERAPY/CHEMORADIOTHERAPY

Findings at surgery are used to determine the need for adjuvant post-operative treatment. For this study, the Sedlis criteria will be reviewed in making recommendation for adjuvant radiotherapy (refer to Appendix 2).

The delivery and management of radiation therapy will be carried out according to local institutional clinical practice guidelines. Preliminary and final dosimetry information as well as concurrent administration of chemotherapy will be recorded. This data will later be analyzed by the study statistician according to the intention to treat principle.

6.8 ACCREDITATION OF PARTICIPATING SURGEONS

Participating surgeons are required to be qualified gynecological oncologists with a proven track record in clinical research and hospital privileges to perform abdominal, laparoscopic, or robotic radical hysterectomy and pelvic lymphadenectomy (for cervical or endometrial cancer), radical trachelectomy or radical parametectomy to qualify as a surgeon for this clinical trial.

In order to minimize surgical complications during a surgeon's initial learning phase, participating gynecologic oncologists must provide evidence to the Trial Management Committee (TMC) of a minimal number of 10 documented cases performed as the main surgeon. Cases will be deidentified to protect the patient confidentiality. The details of the information required should include:

- a. age
- b. BMI
- c. stage
- d. OR time
- e. EBL
- f. Length of stay
- g. Intraoperative complications
- h. Postoperative complications (<30 days)
- i. Red blood cell transfusion requirements (intraoperative and postoperative)

In addition, the prospective Principal Investigator of each site should submit at least 1 unedited video/DVD for approval before submitting to their respective IRB. Each video/DVD will be evaluated and judged by the Trial Management Committee based on the criteria below:

- surgeon technique and tissue handling
- competency in identification and dissection of proper anatomical structures and pelvic spaces
- surgical technique with respect to blood loss and prevention of intraoperative injury
- appropriate decision making based on intraoperative findings
- appropriate use of instrumentation for all parts of the procedure

However, if the institution/investigator has published results and outcomes in peer reviewed literature that demonstrates their skill and technique within this area, then they *may* be exempt from providing the above evidence of their skill.

Once the Principal Investigator is accredited at a site, he/she can then judge the competency of local collaborating surgeons in their institution who wish to enroll patients ensuring the above requirement criteria is met.

Surgeons are not required to have prior experience with lymphatic mapping in order to enroll patients on this study, however skill verification is required. Surgeon skill will be confirmed during the first three cases from each institution. These patients will be excluded from the statistical analyses.

Surgeons who plan to enroll patients and perform the study procedure should be present for the mapping portion of at least one of the first three cases and their presence documented in the operative report. If a surgeon who was not present during one of the first 3 cases wants to enroll a patient and perform the procedure then one of the "verified" surgeons must be scrubbed for the mapping portion of the case. The operative note must include the presence of the verified surgeon during the study procedure.

This process ensures that the surgeon's skill is verified by either 1) scrubbing for one of the first 3 cases or 2) ensuring that a previously verified surgeon is scrubbed for the mapping portion of a case when the patient enrolled after the verification period.

6.9 PATHOLOGY

Every patient will need to have histologically confirmed, adenocarcinoma, squamous cell carcinoma, or adenosquamous carcinoma of the uterine cervix. If biopsy from an apparent cervical cancer demonstrates the presence of sheets of squamous cells without unequivocal stromal invasion, the patient will still be eligible for treatment in the trial if the lesion clinically represents invasive cervical cancer.

